After the family has consented, the recruiter will schedule the parent to complete their baseline research assessment over the phone or notify research staff to send out the survey to those participants who prefer a self-administered format. Families will be told which condition they are in via an email sent by research staff after their Baseline assessment is completed. If the family has been randomly assigned to intervention, they will be informed that a family consultant will reach out to them within one week of their phone interview with additional opportunities for support and coaching. Parents will also be informed that the family consultant will enroll them in the FCU Online program during their first phone call with the parent. If the family has been randomly assigned to the control group, they will be informed that they will be enrolled in the FCU Online one year from now, following participation in the research assessment phone interviews/surveys.

The research assessments will be conducted for all families at baseline, 3-months, 6-months, and 1 year. Each interview/survey is expected to take approximately 1 to 1.5 hours. Families who opted into EARS will be instructed on how to download EARS to their phone at the end of the phone interview or via phone call by assessment staff after self-administered surveys.

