Three months after completing the baseline research assessment, all participants will be contacted to complete their 3-month follow-up research assessment over the phone or as a self-administered survey. Participants in the intervention condition will also complete a brief FCU Online Feedback Survey to assess their experience with the

FCU Online and their Family Consultant. Those who consented to the EARS portion of the research project will be instructed to delete the app from their phone at this time. All families will be contacted 6- months and 1-year later for their final research assessment phone interviews. Families in the control condition will be on-boarded to the FCU Online program at the end of their 1-year phone interview. However, they will not receive Family Consultant coaching.

Materials

3. Clinical trial research study (n=400 parents).

Baseline, 3-mo, 6-mo, 1-year research assessments- Research assessments will be conducted by trained staff as either phone or Zoom interviews or as self-administered surveys (whichever format the parent prefers). If completed as an interview, staff will enter a participant's responses into a Qualtrics survey; if self-administered, the participant will enter a special word provided when the survey link is sent out that will allow research staff to match data with the appropriate ID. Surveys will take between 1 and 1.5 hours, and may be conducted over multiple sessions if needed. Survey items include items about participant demographics, service utilization, family support, health and health behaviors, parenting young children, mental health, and substance use. There is one question in this survey that asks about thoughts of being "better off dead" or of hurting themselves in some way. We have developed a protocol to address the needs of the participant if they answer anything other than "not at all" to this question. Please see "PYC suicide risk assessment protocol."

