Positive parenting: Parents are given information and practice opportunities to build relationships with their child, learn about positive parenting principles, and how to use praise and positive behavior support with their child.

Proactive parenting: Parents are given information and practice opportunities for setting up healthy routines for parents and children, and healthy communication with parents and friends.

Supervision and limit setting: Parents are given information and practice opportunities for managing behavior in toddler years, ignoring unwanted behavior, setting limits, and keeping the home a safe environment.

Website Feedback Survey: The 2-page website feedback survey is administered by an assessor (not Family Consultant) at the time of the 3-month research assessment phone interview/ survey for intervention families. This survey asks questions about the acceptability and usability of the FCU Online, as well as questions

about working with a Family Consultant. This survey will take approximately 15 minutes.

The EARS Tool- During the recruitment phone call, participants will have the option to opt into installing the EARS tool on their phone for an additional \$25. Installation will occur during the baseline phone interview call, or as a separate phone call for those participants who completed the assessment as a self-administered survey. The EARS tool is installed on the participant's phone and has the following functions/capabilities to record naturalistic behavior:

1. Keyboard Logger. This keyboard logger passively collects text input across all applications on the mobile phone. The logger works by installing a specialized keyboard on the phone, which collects every word that the participant types into their phone, including SMS, social media, searching, and emails. The only words that the keyboard does not collect are passwords or any other text typed into a secure field. The output that is generated includes a time, date, and GPS stamp for each entry.
2. Geolocation. We will collect the variation in participants' day-to-day geographical location. This includes assessing the amount of time spent at home compared to other locations each day.

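### An assessor gives an intervention-only feedback survey at the 3-month assessment, which can reveal the family's arm to an outcome interviewer; it should be given separately, once the outcomes are in

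*Protocol*

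**What the plan says.** All of the following is in protocol section C, 3. Clinical trial research study.

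- **Allocation (Methods).** "Families will be told which condition they are in via an email sent by research staff after their Baseline assessment is completed". Parents therefore know their arm from then on, and the outcome interviewer is not the stated channel for telling them.
- **Which arm gets the survey (Methods).** At 3 months, "Participants in the intervention condition will also complete a brief FCU Online Feedback Survey". Control families have nothing equivalent.
- **Who gives it and when (Materials, Website Feedback Survey).** "The 2-page website feedback survey is administered by an assessor (not Family Consultant) at the time of the 3-month research assessment".
- **Content (same entry).** The items cover how acceptable and usable parents found the program, and how they found their consultant. It is expected to last about a quarter of an hour.
- **How outcomes are collected (Materials).** Parents choose a staff interview by phone or Zoom, or a self-administered survey. "If completed as an interview, staff will enter" the responses in Qualtrics. Self-administering families are sent a link. An assessment may be spread over several sessions.
- **One year (Methods).** "Families in the control condition will be on-boarded to the FCU Online program at the end of their 1-year phone interview".

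The protocol text available for this review does not say whether outcome interviewers are blinded, whether the feedback survey follows the outcome items, whether other staff give it, or whether interviewers change between waves. Part of the protocol, from the clinical-trial entry of section H, was not available and could bear on this.

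**The concern.** The outcome interview covers parenting, mental health and substance use. In these areas, the way a question is put, probed or clarified can affect the answer. An interviewer who knows the arm can do this differently for the two groups without meaning to.

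The 3-month data carry weight. SAP Aim 2 gives change from baseline to 3 months as its example of mediator change, and 3- to 12-month change as an example of the outcome trajectory. In the supplement, 3 months is the post-intervention endpoint. Knowledge gained at the 3-month contact could therefore affect the mediator, the later outcomes, or both.

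The protocol already keeps the coach away from the feedback survey. It does not apply the same separation to the person who collects outcomes.

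**Working it through.** The plan gives no figure for interviewer bias, so there is nothing to reproduce. The check is a reading of the passages, followed by a sensitivity illustration.

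**Step 1. Does giving the survey reveal the arm?** Yes. Only intervention families complete it, and it asks about the program and the consultant.

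**Step 2. Does it reveal the arm to the outcome interviewer?** Probably, in interview mode. The survey is tied to the time of the research assessment and given by an assessor. The natural reading is the same person, but the text does not say so.

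**Step 3. Which data are exposed?** This depends on facts that are not stated:

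| Situation | 3-month outcomes | 6-month and 1-year outcomes |
|---|---|---|
| Survey before or between outcome items, interview mode | Exposed | Exposed if the same staff return |
| Survey after all outcome items, interviewer not already aware | Not exposed | Exposed if the same staff return |
| Self-administered outcome assessment | Not exposed | Not exposed |

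The pilot text adds the same survey to the post-test, which suggests that it comes last, but the trial text fixes no order. Because an assessment may run over several sessions, the end of a session is not necessarily the end of the outcome items.

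**Step 4. Sensitivity to an assumed shift.** Let f be the share of assessments affected and b the shift in the arm difference per affected assessment, in SD. Both are assumptions. The average shift is s = f × b. The SAP (Aim 2, Sample size and power) gives 127 per arm, alpha .025 and d = .30. I take the test as two-sided, with no gain from baseline adjustment.

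- SE = √(2/127) = 0.1255; critical value c = 2.241.
- False-positive rate = P(Z > c − s/SE) + P(Z < −c − s/SE).

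| f | b | s | s as a share of d = .30 | False-positive rate (nominal .025) |
|---|---|---|---|---|
| 0.5 | 0.05 | 0.025 | 8% | .028 |
| 0.5 | 0.10 | 0.05 | 17% | .037 |
| 1 | 0.05 | 0.05 | 17% | .037 |
| 1 | 0.10 | 0.10 | 33% | .076 |

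With a baseline correlation of .5, SE falls by √(1 − .25) and the rates for s = 0.05 and 0.10 become .041 and .094. If the survey follows the outcome items and the interviewer did not already know the arm, s at 3 months is zero.

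**The case against.** **Parents know their arm, so blinding the interviewer gains little.** The first part is right, and moving the survey leaves reporting bias untouched. Parents may also mention their Family Consultant during an interview of 1 to 1.5 hours that covers service use and family support. Blinding would be improved, not secured. Interviewer bias is still a separate source, and this part of it is avoidable.

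**The survey may come last, or be given by someone else.** Both are possible. If it comes last, that family's 3-month answers are safe provided the interviewer did not already know the arm, and only carry-over to later waves remains. No passage says that the same staff return, and none says that they do not.

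**The 1-year on-boarding as a second leak.** A reader might infer this, because only control families are on-boarded then. The documents do not support it as it stands: on-boarding comes at the end of the last of four assessments, so disclosure at that point cannot affect that family's data. It matters only if the interviewer is told beforehand which families to on-board.

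**A broken commitment to blinding.** A reader might infer this too. The available text promises no assessor blinding, so this is a design weakness and not a contradiction. Nor does it describe interviewers rating or coding anything; they enter the parent's responses. The plausible route is how questions are asked and clarified.

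**Separate delivery costs nothing.** This has no support. Satisfaction with the program is part of feasibility in SAP Aim 3, and a separate link may draw fewer or more selective replies.

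**Conclusion.** The point holds in a limited form. As written, giving the feedback survey reveals the arm to whoever gives it, and on the natural reading that is an outcome interviewer whenever the assessment is by phone or Zoom. The exposure is at 3 months if the survey precedes or interrupts the outcome items, and at 6 months and 1 year if it follows them and the same staff return.

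The size is unknown. The documents give neither the share of interviews nor any basis for a shift, so the figures above show sensitivity and estimate nothing. A reader might take the upper values (.076, or .094 with baseline adjustment) as the likely inflation. They require every assessment to be affected by an assumed 0.10 SD, and parents may choose self-administration, where no interviewer is involved.

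The change is worth making because it is small, uses a delivery route the protocol already has, and removes an avoidable source of interviewer bias.

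**What to change.** In protocol section C, Materials, Website Feedback Survey:

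- Send the survey as a separate self-administered Qualtrics link, or have staff who do no outcome interviews give it, and only after the 3-month research assessment has been submitted.
- Keep arm out of the outcome interviewers' contact records at 3, 6 and 12 months. As part of this, do not tell the interviewer in advance which families are to be on-boarded at 1 year.
- State whether outcome interviewers are intended to be blinded. If they are, ask them to record any occasion on which a parent discloses the arm.

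**Cost.** This is a wording change plus a separate mailing, using the survey-link route already in place for self-administered assessments. Response to the feedback survey may be somewhat lower, which matters for the satisfaction measure in SAP Aim 3. Staff who do no outcome interviews can follow up non-responders, at the price of some of their time.

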In order to ensure accurate Spanish translation of English materials, we will adopt a translation process in which materials are translated by one translator, reviewed by a second translator who makes corrections and suggestions for improvement and finally reviewed by a third translator who would make a final decision about which version to use when the first two translations differ.

Official Title: "Rural Families Affected by Opioid Use: An Online Parenting Intervention"

And

"Supplement to Prevention Research Center: Parenting Among Women Who are Opioid Users, Project 2"

NCT Number: NCT05180487

Document Date: 9.20.2019

Document: Statistical Analysis Plan

DATA MANAGEMENT AND ANALYSIS

Data analyses and management will be supported in collaboration with the Data Science Core of the PWO Prevention Center, and will rely on resources and support from the center to test complex models associated with the specific aims of the project as well as management of data in the context of the larger dataset associated with the Center. Data management systems similar to those used in our other web-based research projects will be used to ensure the integrity of the analytic results. These systems entail the creation of scheduling algorithms and web-based data collection forms for each instrument. The collection system contains backup and protection routines that ensure confidentiality and preservation of the electronic records.

We will use accepted practices for handling missing data when appropriate. Maximum likelihood methods with time as a random variable, such as the mixed-effects regression models described below, allow the use of all available data and reduce bias associated with attrition and increasing power. These procedures can provide unbiased conclusions even with substantial attrition. We anticipate a participation rate through 12-month follow-up of at least 85% based on our previous FCU school-based efficacy trials and our current rate of participation and retention in our FCU Online randomized trial.

We will compare baseline characteristics of participants across conditions to test for significant differences; characteristics that differ across conditions will be used as covariates in subsequent analyses. Logistic regression analyses will be used to examine potential differences by study condition between dropouts and continuing participants on baseline measures. Attrition analyses will provide information about the external validity of the study, and interaction effects between condition and predictors will provide information about potential confounding effects.

AIM 1: WORK WITH COMMUNITY STAKEHOLDERS IN RURAL OREGON TO EXPAND THE FCU ONLINE TO TARGET EARLY CHILDHOOD (AGES 2-5) AND MOTHERS WITH OPIOID USE AND ADDICTION.

Focus groups and usability testing will be conducted and will be audiorecorded for subsequent transcription. Content analysis techniques will be used to analyze the transcript text from open-ended questions. Coding of text will proceed in two stages. First, a topical indexing coding dictionary will be developed to identify the text pertaining to particular topics generated by focus group and usability testing questions. Data management and data reduction will be supported by use of the ATLAS-ti text-analysis software that supports coding, organization, searching, and retrieval of qualitative data. The software is capable of generating text associated with single or multiple codes, and by

participant characteristics. A more-detailed coding scheme will be developed to capture the content, themes, or sentiment of responses within topics. Specific themes (i.e., content codes) within central concepts will be identified by the evaluation team, and all text pertaining to a specific topic will be coded individually by trained coders. Coder reliability for content will be determined through interrater comparisons of at least 20% of the randomly chosen text in major topical categories. This system of coding will enable us to understand the themes, or issues, related to particular topics, such as barriers to program engagement. It will also enable us to retrieve text illustrating the vocabulary used by participants to describe these issues. Analysis of participants' discourse may reveal statements about, for example, the way they describe program engagement or features that may contribute to intervention modifications. This qualitative data will be categorized into general themes, and the proportions responding to each category will then be tabulated. These responses will be used to evaluate strengths and weaknesses of the intervention approach and to guide further program refinement. [name] has expertise in qualitative approaches to analyses and will be responsible for this aim and analyses associated with our focus group data.

We will assess participant quantitative ratings during the usability testing phase in which the benchmark for acceptable ratings will be mean ratings of 4 or greater on a 5-point scale for each of the SUS items and an overall SUS rating of 80.3, which represents an "A" score. Program acceptability will also be demonstrated by (a) a high level of program usage (e.g., 80% of participants complete the FCU assessment and feedback sessions), and (b) a high degree of consumer satisfaction (e.g., mean ratings > 4 on a 5-point rating scale across satisfaction domains).

AIM 2. EXAMINE THE EFFICACY OF FCU ONLINE FOR RURAL FAMILIES WITH OPIOID USE: MAIN EFFECTS, MEDIATORS, AND MODERATORS.

RESEARCH HYPOTHESES. The hypotheses tested in this aim are (a) families in the intervention condition will show significant improvements on the primary outcomes (child problem behavior and school readiness) and secondary outcomes (parenting skills, parent self-regulation/executive control, and child self regulation/ executive control), compared with families in the control condition; and (b) the putative intervention mechanisms of parenting skills and child self-regulation will mediate (either partially or fully) the association between study condition and the longitudinal trajectories of the primary outcomes. Though we have no specific hypotheses regarding moderating mechanisms, we will also conduct exploratory analyses to examine potential moderators of intervention effects. See Statistical Design component of this proposal for additional information.

We will test whether change in the putative mediating mechanisms of parenting skills and self-regulation (e.g., baseline to 3 months) mediate the association between study conditions and longitudinal trajectories of the primary child outcomes (e.g., overall trajectories, 3- to 12-month change to establish temporal precedence of mediators). Such mediating effects will be tested using the strategies outlined by MacKinnon and Preacher and Hayes. We will assess the joint significance of the indirect pathways (i.e., the joint significance of the pathways from the predictor to the mediating variable and from the mediating variable to the outcome) using the bias-corrected bootstrap test, as recommended by Fritz and MacKinnon. We will also use the bootstrapping technique to test multiple simultaneous mediators proposed by Preacher and Hayes.

The moderation analyses will follow recommendations by Kraemer and colleagues and analytic methods of Aiken and West, Jaccard and Turrisi, and Preacher et al. Each of the potential moderating effects (e.g., child biological sex, race/ethnicity, SES, service utilization; and neonatal abstinence syndrome) will be investigated by conducting the above-mentioned mixed-effects analyses for each outcome that incorporate the Moderator \times Condition interaction term. We have no specific hypotheses for testing sex as a biological variable that would impact outcomes, but we will include sex as a moderator in these analyses. For example, we will test for individual differences in the effect of intervention response (e.g., child problem behavior trajectories) as a function of the participant's value of baseline moderator. Significant moderating effects will be further probed to understand the nature of the conditional relation using computational tools recommended by Preacher et al.

SAMPLE SIZE AND POWER. Using an intent-to-treat approach for the hypothesis of an overall intervention effect, with 127 participants per condition after accounting for 15% attrition across the 12-month assessment period, alpha set to .025 (to adjust for the two outcome domains), there is sufficient power ($>.80$) to detect a condition effect of Cohen's d = .30 or larger. Previous FCU efficacy trials have demonstrated medium-to-large effects for antisocial cigarette use, alcohol use, cannabis use, antisocial behavior, and family conflict. As reported in the prior research section, initial analyses of our ongoing efficacy trial of the FCU Online program demonstrated a medium effect size ($d = .45$) for improvements in child health behaviors, and small-to-medium effect sizes for child social/emotional behavior ($d = .35$), parenting self-efficacy and confidence ($d = .37 - .41$). Given that the effect sizes obtained in the previous FCU efficacy research and the FCU Online preliminary analyses are larger than the power estimates, we should be sufficiently powered to detect meaningful differences between study conditions.

AIM 3. EXAMINE FACTORS RELATED TO SUCCESSFUL UPTAKE AND IMPLEMENTATION.

RESEARCH HYPOTHESES. We will assess the feasibility of the FCU as an Internet-delivered intervention in rural communities with high levels of opioid use, including the extent to which participants engaged in the intervention, completed the program, and were satisfied with the program. We hypothesize that the FCU Online intervention will demonstrate feasibility based on benchmark analyses described below. We also hypothesize that website usage (dosage) and coach fidelity will be associated with significantly greater change in the primary and secondary outcomes.

SAMPLE SIZE AND POWER. With a sample size of 127 in the intervention condition (accounting for 15% attrition), with alpha set to .05 (two-tailed), there is sufficient power ($>.80$) to detect $r = .25$ (moderate effects) for the process analyses involving treatment acceptability, fidelity, and engagement.

Data Management and Analysis for Supplement Pilot Aim

Data management systems similar to those used in our other web-based research projects will be used to ensure the integrity of the analytic results. These systems entail the creation of scheduling algorithms and web-based data collection forms for each instrument, including backup and protection routines that ensure confidentiality and preservation of the electronic records. We will use accepted practices for handling missing data when appropriate. Maximum likelihood methods with time as a random variable, such as the mixed effects regression models described below, allow the use of all available data and reduce bias associated with attrition and increasing power. These procedures can provide unbiased conclusions even with substantial attrition. We anticipate a participation rate through three months of at least 85% based on our previous FCU school-based efficacy trials and our current rate of participation and retention in our FCU Online RCT (90%).

Aim 1: Adapt the FCU Online for young adult parents with a history of substance misuse using a prevention framework

Feasibility. Focus groups and usability testing will be conducted and will be audiorecorded for subsequent transcription. Content analysis techniques will be used to analyze the transcript text from open-ended questions. Coding of text will proceed in two stages. First, a topical indexing coding dictionary will be developed to identify the text pertaining to particular topics generated by focus group and usability testing questions. Data management and data reduction will be supported by use of the ATLAS-ti text-analysis software that supports coding, organization, searching, and retrieval of qualitative data. The software is capable of generating text associated with single or multiple codes, and by

participant characteristics. A more detailed coding scheme will be developed to capture the content, themes, or sentiment of responses within topics. Specific themes (i.e., content codes) within central concepts will be identified by the evaluation team, and all text pertaining to a specific topic will be coded individually by trained coders. Coder reliability for content will be determined through interrater comparisons of at least 20% of the randomly chosen text in major topical categories. This system of coding will enable us to understand the themes, or issues, related to particular topics, such as barriers to program engagement or adverse reactions to the content. It will also enable us to retrieve text illustrating the vocabulary used by participants to describe these issues. Analysis of participants' discourse may reveal statements about, for example, the way they describe program engagement or features that may contribute to intervention modifications. These qualitative data will be categorized into general themes, and the proportions responding to each category will then be tabulated. These responses will be used to evaluate strengths and weaknesses of the intervention approach and to guide further program refinement.

Usability. We will assess participants' quantitative ratings during the usability testing phase in which the benchmark for acceptable ratings will be mean ratings of 4 or greater on a 5-point scale for each of the System Usability Scale (SUS) items and an overall SUS rating of 80.3, which represents an "A" score. Program acceptability will also be demonstrated by (a) high level of program usage (e.g., 80% of participants complete the FCU assessment and feedback sessions), and (b) high degree of consumer satisfaction (e.g., mean ratings > 4 on a 5-point rating scale across satisfaction domains).

Aim 2: Conduct a pilot test of the efficacy of the adapted FCU Online developed in Aim 1.

Statistical design. Individual participants will be randomized to condition and will therefore be the unit of analysis in tests of condition effects in all statistical models. The pilot study will use a pre-post between-group design to examine differences between conditions in the intervention targets assessed at baseline and postintervention (3-month assessment point). Due to the limited sample size and duration of the pilot study, we do not expect to find differences between conditions for the more distal outcomes of opioid misuse or OUD.

Intervention effects and statistical power. We expect that participants receiving the FCU Online intervention will demonstrate improvements in the intervention targets compared to those assigned to the treatment-as-usual control condition. We will examine descriptive statistics and pre-post data to evaluate trends and outcomes, which will provide us with preliminary data to support further research with this population. Mixed-effects regression models will be used to examine post-test differences in the intervention targets between

the two study conditions controlling for baseline levels. With 100 participants and a two-tailed alpha of .05, the pilot study lacks sufficient power ($<.50$) to detect clinically meaningful effects ($d = .30$). As such, we will use the effect size benchmark of $d > .30$ standard deviation units for evaluating intervention effects rather than conducting formal hypothesis testing using $p < .05$. We will evaluate consumer satisfaction surveys after the pilot testing to access acceptability of this model to participants. Program acceptability will also be demonstrated by (a) high level of program usage (e.g., 80% of participants complete the FCU assessment and feedback sessions), and (b) high degree of consumer satisfaction (e.g., mean ratings > 4 on a 5-point rating scale across satisfaction domains). After implementation of the pilot study, we will review results with our stakeholders and obtain feedback on the intervention and outcomes, which will enable us to further refine the model for future uptake and dissemination.

Aim 3: Integrate novel passive sensing and active mobile phone data collection methods into the FCU Online to better understand risk for opioid misuse and points of intervention to reduce risk behavior.

Statistic design and analyses. Analysis of outcomes assessed during the one-week bursts of passive or active data collection methods surrounding each assessment time point will involve alternative mixed-effects models appropriate for measurement-burst study designs. Briefly, subjects (Level 3) will undergo three assessment time points (Level 2). Each time point will involve passive and active data collection methods that generate repeated measures of key study variables at Level 1 (e.g., moment-level affective tone, sleep routines, mood state, coping skills, and stress). The corresponding three variances of these mixed-effects models are between-subjects (BS), within-subjects-between-time points (WS-BTP) and within-subjects-within timepoints (WS-WTP). Unconditional models will describe the degree of BS, WS-BTP, and WS-WTP variability in outcomes. Conditional models will be specified to investigate whether study condition predicts variability in outcomes at each of these levels. Models will include random intercept and time effects to account for individual heterogeneity in levels within and trends across time points, as well as random effects for condition to allow heterogeneity across subjects in effects on outcomes. Because the pilot study is underpowered, we will use standard deviation effect sizes ($d > .30$) as the benchmark for determining clinically meaningful effects.
